# Statistical Analysis Plan

Taisho Pharmaceutical R&D Inc.  
Protocol TS121-US201

Statistical Analysis Plan (SAP)

Final 2.0  
18 Dec 2018  
CONFIDENTIAL

study drug”. In the case of multiple occurrences of the same AEs (at the same SOC and PT level) in an individual patient, the AE with the greatest severity will be reported in Table 14.3.1.2 and the AE with the greatest relationship to study drug will be reported in Table 14.3.1.3.

Serious AEs and EOCs, if any occur, will be summarized [Table 14.3.2.1 and Table 14.3.2.2].

## ***6.3.16.2 Clinical Safety Laboratory Tests (Biochemistry, Hematology and Urinalysis)***

Clinical laboratory biochemistry and hematology results will be presented, using conventional units (original units, received from the laboratory are consistent with CDISC standards) and standard international (SI) units, will be listed by subject number and study time point [Listing 16.2.8.1.1 through Listing 16.2.8.2.2]. Laboratory analyses will utilize scheduled Visit 3 assessments as baseline values. Only if scheduled Visit 3 result is missing will the latest predose assessment be used as the baseline for that patient and test. Change from baseline will be calculated only for laboratory tests with at least one recorded pre-dose assessment.

Certain hematology test samples were assessed by certain sites’ local laboratory and these will be listed together with the corresponding central laboratory results.

Clinical urinalysis and urinalysis microscopic tests will be listed using conventional units [Listing 16.2.8.3].

Laboratory reference ranges, in conventional and SI units will be listed [Listing 16.2.8.4].

All values outside the clinical reference ranges will be flagged in the data listings. The quantitative abnormal values will be flagged with ‘L’ for values below the lower limit of the clinical reference range and ‘H’ for values above the upper limit of the clinical reference range and included in the listings. In addition, certain qualitative tests may be flagged abnormal ‘A’. The Investigator will assess whether the values outside the clinical reference range are clinically significant and laboratory values outside the reference ranges will be reported as abnormal not clinically significant (NCS) or abnormal clinically significant (CS). Clinically significant laboratory values will be recorded by the Investigator as AEs.

Abnormal laboratory values ordered by test category (biochemistry, hematology and urinalysis), randomized treatment, subject number, laboratory test, date and time will be listed using conventional and SI units [Listing 16.2.8.5.1 and Listing 16.2.8.5.2]. Abnormal CS

# Statistical Analysis Plan

Taisho Pharmaceutical R&D Inc.  
Protocol TS121-US201

Statistical Analysis Plan (SAP)

Final 2.0  
18 Dec 2018  
CONFIDENTIAL

laboratory values ordered by test category (biochemistry, hematology and urinalysis), randomized treatment, subject number, laboratory test, date and time will be listed using conventional and SI units [Table 14.3.4.1 and Table 14.3.4.2].

Descriptive statistics (n, mean, SD, SE, CV%, minimum, median and maximum) for non-categorical data including biochemistry, hematology and any quantitative urinalysis will be presented by treatment group and time point for both observed values and changes from baseline in conventional units [Table 14.3.5.1.1] and in SI units [Table 14.3.5.1.2]. Urinalysis categorical results (normal or abnormal) will also be tabulated [Table 14.3.5.2].

Biochemistry, hematology and urinalysis shift tables will be constructed that show the change in quantitative laboratory values (or urinalysis normal/abnormal) from baseline to end of treatment [Table 14.3.5.3.1 through Table 14.3.5.3.3].

Critical ranges for clinically significant laboratory outlier criteria (attached Appendix A) and clinically noteworthy changes (Appendix B) will be used to identify values and trends of potential medical importance. A summary of the number and percentage of patients with clinically significant laboratory outliers, based on Appendix A, for each specified laboratory test will be presented [Table 14.3.5.4.1]. The summary will present across scheduled and unscheduled tests after first dose in Visit 3 and across scheduled and unscheduled test during placebo lead-in period. Clinical laboratory outlier values of individual patients will be presented in a listing [Table 14.3.5.4.2]. Similar analyses will be performed for clinically noteworthy changes from baseline [Table 14.3.5.5.1 and Table 14.3.5.5.2].

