4.4.3 Known and Potential Risks to Human Subjects

Though the relevance to human subjects is not yet fully understood, nonclinical findings suggested that potential risks include cataract, hepatotoxicity, effects on the gastrointestinal system and effects on the renal system. To date, no apparent trends related to these potential risks were noted in the clinical studies.

Treatment emergent ventricular arrhythmias have been reported following single and multiple dose administrations of TS-121. During the SAD study (TS121-US101), two subjects exposed to 2.5 mg of TS-121 had defined intervals of ventricular arrhythmias while on telemetry. Plasma levels were approximately 50% of C_{max} values (40 to 70 ng/mL). The events were without symptoms, resolved without intervention, and produced no residual effects. The events were considered mild in intensity and possibly related to the study drug. One subject was discontinued from the trial, and one subject completed the trial.

In the MAD study (TS121-US102), one subject showed a single episode of 4 consecutive premature ventricular contractions without symptoms while on telemetry approximately 15 hours

after receiving 50 mg dose of TS-121 on Day 9. The investigator assessed the episode as a clinically significant event and described the event as mild and possibly related to TS-121. The subject completed the trial with no additional events.

In a PET receptor occupancy study (TS121-US103), no abnormal ECG results were reported following single TS-121 doses of up to 50 mg. See Sections 8 and 9 of the Investigator's Brochure for additional information.

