Urine Cortisol Level (pooled for 8 hr at home) ^d			Dispense Kit			X						
Inflammatory Markers (TNF-α, IL-1, IL-6, HS-CRP)						X			X			
Pharmacokinetic Blood Sampling ()									X			
Pharmacogenomic Blood Sampling						X						
Placebo administration under single-blind			X ←————→			X						
Randomization						X						
Investigational product dispensing, accountability and compliance check ^e			X			X	X	X	X			
Dose administration under double-blind						X ←————→			X			
Drug adherence (AiCure) ^f			X ←————→						X			
Adverse Event Inquiry & Reporting			X ←————→							X	X	X

A Multicenter, Randomized, Double-blind, Placebo-controlled Study of the Safety and Efficacy of TS-121 as an Adjunctive Treatment for Patients with Major Depressive Disorder with an Inadequate Response to Current Antidepressant Treatment

TS121-US201
Apr 23, 2018
Amendment 4

Procedures	Visit 1**** (Screening) Day -28 to Day -7	Visit 1.1**** (Screening) Day -13 to Day -2	Visit 2 (Start of Placebo Lead-in) Day 1	Visit 2.1 (End of Placebo Lead-in) Day 13 (±2)	Screen* failure ONLY End of Study	Visit 3** (Baseline) Day 15 (+3)	Visit 4 (Week 2) Day 29 (±3)	Visit 5 (Week 4) Day 43 (±3)	Visit 6 (Week 6) Day 57 (±3)	Visit 7 (Follow-up) Day 71 (±3)	ET***	
											ET	Follow Up
Concomitant Medication Inquiry & Reporting	X									X	X	X

* End of Study (Screen failure only): Patients who discontinue between Visits 2 and 3 only will undergo the procedures specified above.

** Visit 3 must be performed after obtaining results for Visit 2.1.

*** The Early Termination (ET) visit should be performed as early as possible after discontinuation. ET follow-up visit will also be necessary approximately 14 days after the patient's last dose.

**** Visit 1 must be performed prior to Visit 1.1.

^a Informed consent for PGx must be obtained prior to blood collection at Visit 3.

^b Ophthalmological Examination: LOCS III assessment must be conducted by an ophthalmologist. Best corrected visual acuity (BCVA) must be performed by the ophthalmologist, optometrist or trained ophthalmic technician. Examination can be performed within -5 days of study Day 1 (Day -5 to Day 1) as Visit 2 assessment.

^c MADRS should be conducted prior to any other mental health assessments and safety/PK/PD assessments.

^d Urinary and Salivary Cortisol: Dispense kits at Visit 2.

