10.5.1.2 Clinical Laboratory Values

Laboratory data from each sampling and changes from baseline will be summarized by descriptive statistics. Laboratory analyses will utilize Visit 3 assessments as baseline values. Parameters will be categorized as low, normal, or high according to the laboratory normal range specifications.

Clinical laboratory outlier criteria will be used to identify values and trends of potential medical importance. A summary for the number and percentage of patients with clinical laboratory outliers for each specified laboratory test will be presented. Similar analyses will be performed for clinically noteworthy changes which would show magnitude of change from baseline.

Criteria for clinical laboratory outliers and clinically noteworthy changes will be described in the SAP.

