# Statistical Analysis Plan

Taisho Pharmaceutical R&D Inc.  
Protocol TS121-US201

Final 2.0  
18 Dec 2018  
CONFIDENTIAL

Statistical Analysis Plan (SAP)

assessment and inventory of symptoms: State versus Trait; Assessability; Face validity; Ecological validity; and Rule of three Ps (pervasive, persistent, and pathological) (SAFER) for confirmation of placebo lead-in eligibility. Results will be communicated to the site prior to Visit 2.

Visit 2 (Start of Placebo Lead-In): Following initial eligibility confirmation, qualified patients will return to the site initiating a 2-week, single-blind placebo lead-in period. An ophthalmologist will conduct a thorough eye examination (including slit lamp under mydriasis). Patients will schedule another phone call for central rater assessments (Visit 2.1), and Visit 3 will be scheduled.

Visit 2.1 (End of Placebo Lead-In): Response to placebo will be assessed using HAM-D by a central rater. The current HAM-D score and change in HAM-D score from Visit 1.1 to Visit 2.1 will be used to determine eligibility.

Visit 3 (Baseline): After completing the placebo lead-in period, patients will return to the site for baseline evaluations. Following confirmation of eligibility, patients will be randomly assigned to receive TS-121 10 mg, 50 mg, or placebo in a 1:1:1 ratio. Patients will be instructed to continue taking investigational product once-daily in the morning and to maintain their current ADT.

Visits 4 (Week 2) and 5 (Week 4): Patients will return to the site for safety and efficacy assessments, dosing compliance, drug accountability and dispensing of a new supply of investigational product. Compliance with the dosing schedule will be assessed. Visit 5 and Visit 6 will be scheduled.

Visit 6 (Week 6): Patients will return to the site for end-of-treatment safety (including ophthalmological examination), efficacy, pharmacokinetic, and exploratory pharmacodynamic assessments and final drug accountability.

End of Treatment (EOT): The EOT visit is Visit 6 for patients who complete treatment and is the last assessment closest to the last treatment day for patients who discontinued from treatment early or failed to complete Visit 6.

Visit 7 (Follow-up): Patients will return to the site for a follow-up evaluation of safety (including ophthalmological examination) and efficacy assessments approximately two weeks after Visit 6.

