### **6.1.3.2 Clinical Laboratory Tests**

Laboratory tests listed in the CSP Section 9.2.7.8 will be performed at times indicated in Schedule of Procedures, Table 1.

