# Statistical Analysis Plan

Taisho Pharmaceutical R&D Inc.  
Protocol TS121-US201

Final 2.0  
18 Dec 2018

Statistical Analysis Plan (SAP)

CONFIDENTIAL

Table 14.3.5.2	Summary of Urinalysis Categorical Results (Safety Analysis Population)
Table 14.3.5.3.1	Shift from Baseline to End of Treatment in Biochemistry Laboratory Results (Safety Analysis Population)
Table 14.3.5.3.2	Shift from Baseline to End of Treatment in Hematology Laboratory Results (Safety Analysis Population)
Table 14.3.5.3.3	Shift from Baseline to End of Treatment in Urinalysis Laboratory Results (Safety Analysis Population)
Table 14.3.5.4.1	Number and Percentage of Patients With Clinical Laboratory Outlier Values (Safety Analysis Population) (Safety Analysis Population)
Table 14.3.5.4.2	Individual Patients with Clinical Laboratory Outlier Values (in Conventional Units) (Safety Analysis Population)
Table 14.3.5.5.1	Number and Percentage of Patients With Clinically Noteworthy Laboratory Changes (Safety Analysis Population)
Table 14.3.5.5.2	Individual Patients with Clinically Noteworthy Laboratory Changes (in Conventional Units) (Safety Analysis Population)

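### The laboratory shift tables run only from baseline to end of treatment, so mild out-of-range changes at Week 2 or 4 that resolve have no categorical count by arm

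*SAP*

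**What the plan says.** SAP 6.3.16.2 plans three reference-range shift tables, 14.3.5.3.1 (biochemistry), 14.3.5.3.2 (hematology) and 14.3.5.3.3 (urinalysis): "shift tables will be constructed that show the change in quantitative laboratory values (or urinalysis normal/abnormal) from baseline to end of treatment". The titles in SAP Table 2 repeat the same contrast. No shift to the worst post-baseline value is planned.

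SAP 6.1.3.2 says that laboratory tests "will be performed at times indicated in Schedule of Procedures, Table 1". That schedule has post-baseline samples at Visits 4, 5 and 6 (Weeks 2, 4 and 6), Visit 7, early termination (ET) and ET follow-up. Protocol 10.5.1.2 does not tie the reference-range categories to one visit: "Parameters will be categorized as low, normal, or high according to the laboratory normal range specifications".

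SAP Section 1 defines EOT as Visit 6 for completers. For others it "is the last assessment closest to the last treatment day for patients who discontinued from treatment early". Of the ET visit, Protocol 9.1 says: "The Early Termination (ET) visit should be performed as early as possible after discontinuation". It sets no day limit.

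The same SAP section plans other laboratory outputs. Of the Appendix A outlier counts it says: "The summary will present across scheduled and unscheduled tests after first dose in Visit 3". Similar analyses are planned for the Appendix B changes from baseline. There are also by-visit descriptive statistics, an eDISH table and plots, and flagged listings.

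**The concern.** Safety and tolerability against placebo is the first-listed primary objective. Protocol 4.4.3 says the nonclinical findings suggest that "potential risks include cataract, hepatotoxicity, effects on the gastrointestinal system and effects on the renal system". A shift table is the usual place to read how many patients in each arm moved from normal to high or low. Here it uses one of the three scheduled on-treatment samples per completer, so any movement at Week 2 or 4 that has reversed by Week 6 disappears from it. The SAP describes the trial as a pilot whose results will support future studies, so mild, reversible changes by dose are information worth having. The question is how much of this the other planned tables already supply.

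**Working it through.** No figure in the plan bears on this point, so the check compares what each output counts.

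**Assumptions.** Shift categories are low, normal and high, taken from Protocol 10.5.1.2 because the SAP does not define them. The Appendix B table uses the same window as the Appendix A table (all scheduled and unscheduled tests after the first randomized dose), because the SAP calls the analyses similar.

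**Step 1: markers that Appendix B judges by a ratio to baseline.** Take a patient with an in-range baseline B and a transient peak P, both in multiples of ULN, who is back in range at EOT. The shift table shows nothing. Appendix B counts the patient if P > k x B. A true normal-to-high rise (P > 1) therefore escapes only if 1 < P <= k x B, which requires B > 1/k. Since B <= 1, the largest uncounted peak is k x ULN, which lies below the Appendix A limit wherever both rows exist.

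| Marker | Appendix A | Appendix B | Baseline at which a rise can escape | Highest uncounted peak |
|---|---|---|---|---|
| ALT, AST | >2.5 x ULN | >1.5 x baseline | above 1/1.5 = 0.67 x ULN | 1.5 x ULN |
| Creatinine | >1.5 x ULN | >1.33 x baseline | above 1/1.33 = 0.75 x ULN | 1.33 x ULN |
| Bilirubin | >1.5 x ULN | >1.25 x baseline | above 1/1.25 = 0.80 x ULN | 1.25 x ULN |
| BUN | no row | >1.2 x baseline | above 1/1.2 = 0.83 x ULN | 1.2 x ULN |
| GGT | >2.5 x ULN | no row | any in-range baseline | 2.5 x ULN |

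Example: ALT going from 0.9 to 1.3 x ULN is a ratio of 1.3/0.9 = 1.44. This is below 1.5, and 1.3 is below 2.5, so neither appendix counts it.

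**Step 2: markers that Appendix B counts only from an abnormal baseline.** For sodium, potassium, chloride, calcium, glucose, WBC and platelets, every Appendix B criterion starts from a baseline at or beyond a reference limit. A patient with a baseline inside the range cannot be counted there, so only Appendix A remains:

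- Sodium: <130 or >150 mEq/L
- Potassium: <3.0 or >5.5 mEq/L
- Calcium: <8.0 or >11.5 mg/dL
- Glucose: <55 or >160 mg/dL
- Leukocytes: <3.0 x10^3/μL (no row for an increase)
- Platelets: <75 x10^3/μL (no row for an increase)
- Chloride: no row

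A platelet count that falls from normal to anywhere from 75 up to the lower limit of normal, and recovers by Week 6, therefore enters no categorical count. The documents give no reference ranges, so the width of these bands cannot be stated.

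**Step 3: whether another output supplies the count.**

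- By-visit statistics give means and extremes by arm, not numbers of patients who shifted.
- Listings flag every out-of-range value but give no rates.
- The peak-value figures (14.3.2.1 and 14.3.2.2) show each patient's maximum ALT, AST and bilirubin with no threshold, but they pool the two TS-121 doses and have no renal counterpart.
- The eDISH table needs ALT or AST >3 x ULN or bilirubin >2 x ULN.
- Adverse event tables depend on the investigator judging the value clinically significant.
- Urinalysis normal/abnormal results are also tabulated (Table 14.3.5.2), but that table is not described as a shift from baseline.

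**The case against.** The strongest reply is that the shift tables are one of several complementary outputs in a pilot study. Because Appendix B sets no reference limit for the liver and renal markers it lists, it is more inclusive than a shift table for most patients: any rise beyond the ratio is counted, at whichever visit it occurs. The peak-value plots already give a worst-post-baseline display of ALT, AST and bilirubin beside placebo. Protocol 10.5.1.2 asks for categories, not for a worst-value shift table. All of this stands, and it confines the gap to the changes in Steps 1 and 2.

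A reader might still infer that transient liver or renal elevations between the ULN and the outlier limit are never counted by arm. The documents do not support that, because Appendix B counts most of them.

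A reader might also infer that patients stopped for an abnormality are classified on a recovering ET value, and that this flatters the more toxic arm. The SAP's EOT wording does not settle whether the last on-treatment sample or the ET sample is used, and the ET visit is meant to be prompt. An event that leads to discontinuation is to be treated as an adverse event (Protocol 11.1.1), and the adverse event overview reports such events by arm (SAP 6.3.16.1). The direction of any bias is conjecture. The ambiguity in the EOT sample is real and should be removed.

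**Conclusion.** The point holds in limited form. Tables 14.3.5.3.1 to 14.3.5.3.3 cannot show an out-of-range change that resolves before EOT. For larger transient liver and renal changes this costs little, since other planned outputs count or display them. What lacks a by-arm categorical count is the set of mild rises from high-normal baselines, GGT up to 2.5 x ULN, and shifts from a normal baseline in the seven Step 2 markers that do not meet an Appendix A criterion.

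It might be tempting to turn the use of one visit in three into a share of signal lost. The documents say nothing about how long an elevation lasts, and any such share would describe one table rather than the whole safety report, so no percentage is given. The conclusion rests on the low/normal/high categories and on Appendix B sharing the Appendix A window. It is a reporting improvement worth making because it is cheap, not a failure to detect hepatotoxicity or renal toxicity.

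**What to change.** In SAP 6.3.16.2 and SAP Table 2:

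1. Add to Tables 14.3.5.3.1 to 14.3.5.3.3 a shift from baseline to the worst post-baseline category by treatment arm, with the two TS-121 doses separate. Show highest and lowest category separately, and normal/abnormal for urinalysis.
2. Use scheduled and unscheduled results after the first randomized dose, the same window as Table 14.3.5.4.1, so that the counts agree. State this as an exception to SAP 6.3.1, which otherwise allows one assessment per time point and takes the first of any post-dose repeats.
3. Define the shift categories, and keep the baseline-to-EOT shift as a second panel.
4. State which sample is the EOT value for early discontinuers: the last on-treatment sample or the ET sample.

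The cost is SAP wording, minor programming and larger tables. All the data are already collected, and no visit, test or clinical rule changes.

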 13. Patients who are undergoing treatment with drugs that might influence HPA axis function, including psychotropic medications, benzodiazepines, metyrapone, lithium and/or corticosteroids
[Please refer to Section 8.3 for a more detailed list of prohibited concomitant medications]
 14. Patients who need/plan to take moderate to strong CYP3A4 inhibitors/inducers (food, beverages, medications and supplements) during this study (see Appendix 1)
 15. Patients who work night shifts or need to work night shifts during the trial
 16. Females who are pregnant, intend to become pregnant (within 90 days of the last dose), or who are breastfeeding
 17. Patients with significant hepatic, renal, cardiovascular, hemodynamic, pulmonary, gastrointestinal, hematological, locomotor, immunologic, ophthalmologic, metabolic, neurological, or endocrine disease that in the opinion of the investigator would confound participation or study results

18. Patients with clinically significant ECG* findings at Visit 1 or Visit 3, or hematology, biochemistry, or urinalysis abnormalities at Visit 1 (abnormal laboratory values considered to be not clinically significant as per the investigator are acceptable)
[* Note: QTcF interval of > 450 msec in males or > 470 msec in females, will be the basis for exclusion from the study; ECG may be repeated once for confirmatory purposes, if an initial value is obtained that exceeds the values specified]
19. Patients with history or presence of cataract (lens opacities with vision disturbances), glaucoma, chronic inflammatory eye disease, significant eye trauma, any ophthalmic surgical procedure (e.g. cataract or glaucoma) or any ocular laser surgery in either eye
20. Patients with lens opacity based on ophthalmological examination performed at Visit 2 as listed below:
- Nuclear opalescence (NO) with a LOCSIII classification > 3.0 in either eye
 - Nuclear color (NC) with a LOCSIII classification > 3.5 in either eye
 - Cortical lens opacities (C) with a LOCSIII classification > 2.0 in either eye
 - Posterior subcapsular lens opacities (P) with a LOCSIII classification > 0.3 in either eye
21. Patients with a history (within 5 years) or presence of malignancy at Visit 1
[Note: History (within 5 years) of non-metastatic, non-progressive basal and/or squamous cell carcinoma of the skin, in situ cervical and prostate cancer are exceptions (currently in remission)]

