9.2.7.8.2 Biochemistry

Blood samples will be drawn under fed or fasted conditions for routine biochemistry at specified visits indicated in Section 9.1. Last meal time will be recorded in the patient's study source records and captured electronically.

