### **6.3.16.4 12-Lead Electrocardiogram**

Electrocardiogram data (ventricular rate, RR, PR, QT, QTcB and QTcF interval data, QRS duration) will be listed [Listing 16.2.9.2.1] with the Investigator interpretation. Any QTcF or QTcB  $>500$  msec will be flagged in the listing. Electrocardiogram data change from baseline will be listed [Listing 16.2.9.2.2] and each flagged to distinguish QTc change from baseline 30 to 60 msec or  $>60$  msec.

Descriptive summaries (n, mean, SD, SE, CV%, minimum, median and maximum) of interval data observed values and change from baseline will be presented by treatment and time point [Table 14.3.6.2.1 and Table 14.3.6.2.2]. Baseline is defined as the scheduled predose assessment of Visit 3. Only if scheduled Visit 3 result is missing, will the latest predose assessment be used as the baseline for that subject number and test.

The categorical analysis of QTcB and QTcF will be presented in a frequency table of patients categorized based on maximum post-baseline QTc ( $\leq 500$  msec or  $>500$  msec) and maximum change from baseline ( $<30$  msec, 30 to 60 msec, and  $>60$  msec) [Table 14.3.6.2.3].

The incidence of abnormalities, based on the clinical interpretations from the Investigator, will be enumerated by treatment group and visit [Table 14.3.6.2.4].

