## APPENDIX A: CLINICALLY SIGNIFICANT LABORATORY OUTLIER CRITERIA

Outlier Criteria [a]		
Analyte	SI Units	Conventional Units
HEMATOLOGY		
Hemoglobin (increase)	Value >2 mmol/L above the ULN	Value >2 g/dL above the ULN
Hemoglobin (decrease)	Value <6.2 mmol/L	Value <10 g/dL
Leukocytes (decrease)	Value <3.0 x10  /L	Value <3.0 x10  /μL
Lymphocytes (increase)	Value >4.0 x10  /L	Value >4.0 x10  /μL
Lymphocytes (decrease)	Value <0.8 x10  /L	Value <0.8 x10  /μL
Neutrophils (decrease)	Value <1.5 x10  /L	Value <1.5 x10  /μL
Platelets (decrease)	Value <75 x10  /L	Value <75 x10  /μL
BIOCHEMISTRY		
Albumin (decrease)	Value <30 g/L	Value <3 g/dL
Alkaline phosphatase (increase)	Value >2.5 xULN	Value >2.5 xULN
ALT (increase)	Value >2.5 xULN	Value >2.5 xULN
AST (increase)	Value >2.5 xULN	Value >2.5 xULN
Bicarbonate (decrease)	Value <16 mmol/L	Value <16 mEq/L
Bilirubin (increase)	Value >1.5 xULN	Value >1.5 xULN
Calcium (decrease)	Value <2.0 mmol/L	Value <8.0 mg/dL
Calcium (increase)	Value >2.9 mmol/L	Value >11.5 mg/dL
Cholesterol (increase)	Value >7.75 mmol/L	Value >300 mg/dL
CPK (increase)	Value >2.5 xULN	Value >2.5 xULN
Creatinine (increase)	Value >1.5 xULN	Value >1.5 xULN
GGT (increase)	Value >2.5 xULN	Value >2.5 xULN
Glucose (decrease)	Value <3.0 mmol/L	Value <55 mg/dL
Glucose (increase)	Value >8.9 mmol/L	Value >160 mg/dL
Magnesium (decrease)	Value <0.5 mmol/L	Value <1.2 mg/dL
Magnesium (increase)	Value >1.23 mmol/L	Value >3.0 mg/dL
Phosphate (decrease)	Value <0.8 mmol/L	Value <2.5 mg/dL
Potassium (decrease)	Value < 3.0 mmol/L	Value < 3.0 mEq/L
Potassium (increase)	Value >5.5 mmol/L	Value >5.5 Meq/L
Sodium (decrease)	Value <130 mmol/L	Value <130 mEq/L
Sodium (increase)	Value >150 mmol/L	Value >150 mEq/L
Triglycerides (increase)	Value >2.5 xULN	Value >2.5 xULN
Uric acid (increase)	Value >0.59 mmol/L	Value >10 mg/dL
URINALYSIS		
Hemoglobin, urine (increase)	Present	Present
Protein, urine (increase)	Result of 2+ or 3+	Result of 2+ or 3+

Notes: LLN = lower limit of normal range; ULN = upper limit of normal range; ALT = alanine aminotransferase; AST = aspartate aminotransferase; CPK = creatine phosphokinase; GGT = gamma-glutamyl transpeptidase.

[a] Outlier values based on Grade 2 (moderate) or higher from the Common Toxicity Criteria for Adverse Events v3.0 (CTCAE) Publish Date: August 9, 2006.

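### The laboratory outlier table ignores Visit 3 status, so patients already beyond an Appendix A limit before randomized dosing enter the by-arm post-dose counts

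*SAP*

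**What the plan says.** SAP 6.3.16.2 plans a summary in Table 14.3.5.4.1 of the "number and percentage of patients with clinically significant laboratory outliers, based on Appendix A, for each specified laboratory test". The time frame is set in the next sentence: "The summary will present across scheduled and unscheduled tests after first dose in Visit 3", with a second summary "across scheduled and unscheduled test during placebo lead-in period".

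Appendix A states each criterion as a level, for example "Value >2.5 xULN" for ALT, AST, GGT, CPK and triglycerides. Its footnote explains the origin: "Outlier values based on Grade 2 (moderate) or higher from the Common Toxicity Criteria for Adverse Events v3.0". The row labels (increase, decrease) give the direction of the limit. They do not require a change from the patient's own value.

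SAP 6.3.16.2 makes Visit 3 the laboratory baseline, but the outlier rule does not refer to it. Patients can be randomized with abnormal values: under exclusion criterion 18 in Protocol 7.1.2, which looks at laboratory results from Visit 1, "abnormal laboratory values considered to be not clinically significant as per the investigator are acceptable".

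**The concern.** A post-dose outlier count by arm is read as a count of what happened on treatment. Here it mixes two groups: patients who crossed the limit after randomized dosing began, and patients who were beyond it at Visit 3 and did not change. The SAP separates these groups for adverse events. In 6.3.16.1 an event is treatment-emergent only if it was absent before the first randomized dose or became more severe. The outlier table has no matching condition.

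Safety against placebo is a primary objective, and Protocol 4.4.3 names liver and kidney effects among the potential risks. With about 60 patients per arm, a few carried-over patients can make up much of a small count, blur a real difference between arms, or create an apparent one by chance.

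**Working it through.** The documents give no figure for this point, so there is nothing to reproduce. The check has three parts.

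**1. Does any other output supply the missing baseline condition?**

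- *Appendix B (noteworthy changes, Tables 14.3.5.5.1 and 14.3.5.5.2).* Appendix A has 32 criteria on 25 analytes, and Appendix B has 20 analytes. Matched row by row, 15 are shared and 25 − 15 = 10 Appendix A analytes have no Appendix B criterion: lymphocytes, bicarbonate, cholesterol, GGT, magnesium, phosphate, triglycerides, uric acid, urine hemoglobin and urine protein. For six of the shared 15 (white cells, platelets, glucose, sodium, potassium, calcium), every Appendix B condition starts from a baseline at or beyond a reference limit. A patient who moves from mid-normal to an outlier meets none of them. That leaves 15 − 6 = 9 analytes with a change rule that a patient with a normal baseline can meet.
- *Shift tables (14.3.5.3.1 to 14.3.5.3.3).* These run from baseline to end of treatment only. Blood tests are classed as low, normal or high by reference range (Protocol 10.5.1.2). A patient who goes from 1.2 × ULN to 3 × ULN reads high to high, as does one at 3 × ULN throughout. Urinalysis shifts are normal to abnormal, which is close to the Appendix A rule for urine hemoglobin.
- *Lead-in summary.* The schedule (Protocol 9.1, SAP Table 1) has no clinical laboratory test at Visit 2 or 2.1, and SAP 6.3.1 places Visit 3 in the treatment period. In any case, a separate lead-in count removes no one from the post-dose count.

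One wording point needs reconciling. The outlier sentence places the first dose in Visit 3, while footnote e of the schedule starts randomized dosing the morning after. On either reading, the Visit 3 laboratory values precede the first randomized dose if drawn before it, and SAP 6.3.16.2 treats them as baseline.

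**2. Chance imbalance**

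Inputs: n = 60 per arm (Protocol synopsis); p0 = share of patients beyond a given limit at Visit 3 who stay beyond it (assumed).

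Expected carried-over patients per arm = 60 × p0. The chance that two arms differ by 3 or more is the sum of P(X = i) × P(Y = j) over all |i − j| ≥ 3, with X and Y independent Binomial(60, p0).

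| p0 (assumed) | Expected per arm | P(differ by 3 or more) |
|---|---|---|
| 0.5% | 0.3 | 0.5% |
| 1% | 0.6 | 2.7% |
| 2% | 1.2 | 9.7% |
| 5% | 3.0 | 28.7% |
| 10% | 6.0 | 44.3% |

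**3. Dilution**

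Here p0 is the share beyond the limit at Visit 3, s the share of those still beyond it post-dose, and e the new-onset rate among the rest. All three are assumed, with e = 2% on placebo and 8% on TS-121.

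Proportion counted = p0 × s + (1 − p0) × e.

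- p0 = 1%, s = 0.5: placebo 0.005 + 0.99 × 0.02 = 2.5%; TS-121 0.005 + 0.99 × 0.08 = 8.4%; ratio 3.4.
- p0 = 5%, s = 0.9: 0.045 + 0.95 × 0.02 = 6.4% against 0.045 + 0.95 × 0.08 = 12.1%; ratio 1.9.
- p0 = 10%, s = 0.9: 0.09 + 0.90 × 0.02 = 10.8% against 0.09 + 0.90 × 0.08 = 16.2%; ratio 1.5.

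Among patients not beyond the limit at Visit 3, the contrast is 2% against 8% (ratio 4.0) in every case. The carried-over share of the placebo count is 20%, 70% and 83% in the three cases. The absolute difference suffers less: 5.9, 5.7 and 5.4 percentage points against 6.0.

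**The case against.** The strongest reply is that level and change are separated on purpose. Protocol 10.5.1.2 plans outliers by level and, next to them, noteworthy changes that show the size of the move from baseline. The SAP follows that plan and never calls a level outlier treatment-emergent. Laboratory values judged clinically significant are also recorded as adverse events, where the new-or-worsened rule applies. Change-from-baseline statistics by arm and visit, patient-level outlier output and full listings are planned too. All of this stands, and it limits the harm. It does not make the by-arm outlier count interpretable, because the change criteria reach only part of Appendix A and the adverse-event route depends on the investigator's judgement.

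The prevalence is also assumed. Limits at Grade 2 or above, in a population screened for significant disease, will be rare at Visit 3 for tests such as platelets or sodium. The upper rows of the chance-imbalance table should not be applied to every test.

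A reader might infer that the ECG interpretation table has the same fault. The documents do not support that: "The incidence of abnormalities, based on the clinical interpretations from the Investigator, will be enumerated by treatment group and visit". ECGs are recorded at Visit 3, so a by-visit table can show the baseline frequency in each arm beside the later visits and does not pool post-dose results. Clinically significant ECG findings at Visit 1 or 3 are an exclusion, and later ones become adverse events.

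A reader might also want glucose and triglycerides split by meal state, since "Blood samples will be drawn under fed or fasted conditions for routine biochemistry" and the last-meal time is recorded. That is a separate question, and the documents give no fasting cut-off on which to base a split.

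**Conclusion.** The point holds as a weakness of one descriptive safety table that is cheap to improve. Table 14.3.5.4.1 counts patients with any post-dose value beyond an absolute limit, whatever their Visit 3 status. The effect is larger counts, a diluted ratio between arms and added chance imbalance. For a single test in two arms of 60, the chance of a carried-over difference of 3 or more patients runs from about 3% at an assumed prevalence of 1% to 44% at 10%. These figures assume that every baseline outlier persists; with partial persistence, the effective prevalence is lower.

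Two stronger readings are tempting and are not supported. One is that the table is biased for or against TS-121: pre-existing values are balanced on average by randomization, so no direction follows. The other is that nothing else in the plan compares outliers with baseline: for 9 of the 25 analytes Appendix B does so even from a normal baseline, although for hemoglobin it covers only decreases, and the urinalysis shift comes close for urine hemoglobin at end of treatment. The gap is widest for the 10 analytes with no change criterion, GGT, urine protein and triglycerides among them, and next for the six that need an abnormal baseline.

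**What to change.** In SAP 6.3.16.2 and the table shell, present Table 14.3.5.4.1 by Visit 3 outlier status for each test and arm:

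- (a) patients with a new post-dose outlier among those not beyond that limit at baseline, with that group as the denominator;
- (b) patients already beyond the limit at baseline, shown separately, with the number whose post-dose value is worse than their baseline value;
- (c) the overall count as now planned.

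Part (b) is needed because a count of new outliers alone would lose patients who start beyond the limit and get worse, and for GGT or triglycerides no Appendix B row would pick them up. The SAP should use its existing baseline rule (scheduled Visit 3, or the latest pre-dose value if that is missing) and say how patients without a baseline value are shown.

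The cost is wording and one more split in the table, with smaller denominators in (a) and very small ones in (b). No new data are needed.
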